An important non-pharmacologic intervention for SCD is RBC transfusion.³ RBC transfusions are indicated for severe symptomatic anemia, acute complications like stroke or acute multi-organ failure, and/or secondary prevention of stroke or recurrent pain crises in individuals with SCD.³ The two primary types of RBC transfusions, simple (addition of RBCs without removal of the patient's blood) and exchange (removal of the patient's blood and replacement with donor packed RBCs), have both acute and chronic indications. Treatment guidelines recommend acute transfusions for symptomatic anemia, ACS, multiorgan failure, and preoperatively; chronic transfusions, usually administered monthly,

are recommended for stroke prevention.³ While blood transfusions can improve SCD complications, they are also associated with important risks that can occur at each transfusion: resultant iron overload can lead to end organ damage, alloimmunization can lead to delayed hemolytic transfusion reactions (DHTR) and mortality, and transfusion transmitted infections can cause organ damage and mortality.^{3,8–11} Additionally, transfusion administration can be burdensome to patients due to the need for frequent venous access, which can cause pain, psychological distress, and interruptions to daily life.¹² A significant unmet need exists for new therapies and interventions that address the clinical complications of SCD while mitigating the patient burden.

Once-daily oral administration of voxelotor has been shown to reduce red-cell sickling, blood viscosity and improve red-cell deformability in vitro and to extend red-cell half-life and reduce anemia and hemolysis in vivo. ¹³ Evidence from clinical studies has demonstrated that voxelotor has a beneficial effect on Hb levels, a critical factor in the decision for an RBC transfusion. However, no clinical trials have demonstrated the impact of voxelotor on rates of RBC transfusion. While preliminary real-world evidence (RWE) supports a reduction in RBC transfusions associated with voxelotor use, these studies are limited by small sample sizes and lack of comparator populations. ^{14,15}

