Region	Baseline Characteristic; Covariate	[Index]	Frequency and proportion (N, %) Categorical: Northeast, Midwest, South, and West Regions (based on Census geographic regions), Missing
Top 10 Diagnosing Provider Specialty	Baseline Characteristic; Covariate	[Baseline]	Frequency and proportion (N, %) [Provider specialty categories will be included in statistical analysis plan (SAP)]
SCD Hematology Diagnosing Provider	Baseline Characteristic; Covariate	[Baseline]	Frequency and proportion (N, %) Binary: Yes, No (including non-hematology and null values)
SCD Genotype ¹	Baseline Characteristic	[Baseline]	Frequency and proportion (N, %) Categorical: Homozygous SS, HbSC, HbSB0 thalassemia, HbSB+ thalassemia, Unknown, Multiple genotypes reported
Comorbidities – SCD specific morbidities ²	Baseline Characteristic; Covariate	[Baseline]	Frequency and proportion (N, %)
Hydroxyurea	Baseline Characteristic; Covariate	[Baseline]; [Follow- up]	Frequency and proportion (N, %)
Crizanlizumab	Baseline Characteristic; Covariate	[Baseline]; [Follow- up]	Frequency and proportion (N, %)
L-glutamine	Baseline Characteristic; Covariate	[Baseline]; [Follow- up]	Frequency and proportion (N, %)
Erythropoietin Stimulating Agent (ESA)	Baseline Characteristic; Covariate	[Baseline]; [Follow- up]	Frequency and proportion (N, %)

V2.0 23 December 2024			
RBC transfusion	Baseline Characteristic; Covariate	[Baseline]; [Follow-up]	Continuous: Mean (SD); Median (IQR); Minimum; Maximum.
Baseline Hb lab test	Baseline Characteristic	[Baseline]	Frequency and proportion (N, %) Categorical: Komodo lab test only, Quest lab test only, Komodo lab test and Quest lab test, No value
Baseline Hb value ³	Baseline Characteristic	[Baseline]	Continuous: Mean (SD); Median (IQR); Minimum; Maximum.
Charlson Comorbidity Index (CCI) ⁴	Baseline Characteristic; Covariate	[Baseline]	Continuous: Mean (SD); Median (IQR); Minimum; Maximum. Frequency and proportion (N, %) For individual categories see SAP.
Healthcare Interactions - Inpatient/Outpatient Visit	Baseline Characteristic; Covariate	[Baseline]	Continuous: Mean (SD); Median (IQR); Minimum; Maximum.
Follow-up time	Baseline Characteristic; Covariate	[Follow-up]	Continuous: Mean (SD); Median (IQR); Minimum; Maximum.
Voxelotor	Exposure	[Index]; [Follow-up]	Frequency and proportion (N, %)
Iron overload	Baseline Characteristic; Covariate	[Baseline]	Frequency and proportion (N, %)

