9.7.2. Baseline Balance

PS methods will be used to account for baseline balance of covariates between the treated group and matched controls. PS adjustment allows for the inclusion of a pre-defined comprehensive list of confounding covariates to ensure comparable exposure and referent groups, avoiding non-convergent issues of standard outcome models. PS models estimating the ATT will be considered for this analysis. An iterative approach to estimating the PS will be used.

PS Estimation

Potential covariates that affect treatment decisions or outcomes and are eligible for inclusion in the PS model are listed in Table 5.³⁰ Potential confounding covariates will be assessed for balance at baseline using absolute standard differences (ASD). Covariates with an ASD > 0.1 will be considered imbalanced and will be included in a PS model fit using logistic regression. With this approach, the PS will be modeled as the conditional probability of receiving voxelotor given the selected covariates for each individual. The PS modeling will be performed blinded of any outcome to ensure endpoints will not be assessed before a PS method is selected. Diagnostic criteria used to assess PS model estimate are described below and in Table 6. Multiple iterations of the PS model estimation may be performed depending on diagnostic evaluation results.

Use of PS in Baseline Confounder Balance

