Multiple PS methods will be considered and a step-wise approach will be used to select the most appropriate method. PS matching, in which voxelotor-exposed individuals are matched to unexposed patients using variable-ratio (1:2) greedy nearest neighbor matching with a caliper, will be the primary approach.³¹ If the sample size falls below the minimum required sample size for the primary and secondary endpoint to be 80% powered during the matching process, weighting methods, such standardized mortality/morbidity ratio (SMR) weights, will be evaluated for their suitability and to preserve sample size of the exposed group. With the SMR approach, weights for the voxelotor group are equal to 1; weights for the referent arm are defined as PS/(1-PS). The distribution of SMR weights will be reviewed; truncation and trimming will be considered to account for extreme weights. If neither PS model type is deemed appropriate, a non-ATT model (overlap weights) will be considered. With the overlap approach, overlap weights are defined as 1-PS in the voxelotor arm; weights for individuals in the referent arm are defined as the PS. The distribution of overlap weights will be reviewed to evaluate the appropriate trimming threshold. PS-matching and weighting methods will be further described in the SAP.

Diagnostic Evaluation of PS Methods

An *a priori* list of diagnostic criteria will be set to ensure analytic assumptions are met before a PS method is selected. For example, ASD will be used to assess the comparability of the groups before and after the application of PS methods.³² Observations for any covariate leading to zero cells in either group may lead to an inadequate overlap between groups in

their PS distributions. Therefore, collapsing similar categories within variables if there are categories with frequencies <10% to minimize concerns for non-positivity will be considered. Further, variables with substantial non-positivity may be removed from the model (i.e., covariables with very low or zero values in either group). Patients with missing information for covariables may be excluded or imputed from the analysis set depending on the degree of missingness and the variable. When applicable, a robust variance estimator may be utilized in the outcome model(s) to account for the weighted design. Demographics and baseline clinical characteristics of patients within each study group will be described before and after the applications of PS adjustment.

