The diagnostic results will be presented to the study team who will provide a final confirmation that all the necessary criteria have been satisfied. The inferential analysis phase will only begin after sign-off of the final protocol by the study team, certified by the Principal investigator (PI). More information on the methods used to balance baseline covariates can be found in SAP and in Table 6 below.

Table 6. Diagnostic Checklist

#	Diagnostic	Description	1
1	Confirm positivity of variables	PS distribution will be visually inspected and overlap in all areas of the PS distribution will be confirmed.	
		Additionally, any patients with an observation for covariates not meeting the positivity assumption and may be considered outliers. Further detail on methodology is available in SAP.	
2	Confirm PS model fit	Any covariate with no variability (i.e., a constant value across all observations) will be removed from the PS model. The PS model will be determined as not overfit if each covariate contains ≥ 12 exposed subjects. ³³ Collinear covariates will be defined as any covariates with a Pearson correlation coefficient greater than or equal to 0.7. ³⁴ Collinear variables may be removed from the PS model if large standard errors are observed because including them may lead to biased coefficient estimates. If removed, the model will be refitted. ³⁵	
3	Confirm baseline confounder balance	Balance of all potential confounders (i.e., covariates) will be confirmed for voxelotor vs referent patients. Covariate balance will be defined as an ASD ≤ 0.10. ³⁶ Balance of these variables will still be confirmed after PS matching. Should any variables with small residual imbalance remain, balance may be deemed acceptable if the variable is not a predictor of the outcome among the referent group (defined as an ASD < 0.10 when comparing the risk of the outcome to those with the variable versus those without it). This determination will be made by clinical experts or key opinion leaders on the study team. Evaluation of imbalance in outcome prediction will only be	

1/2	0	23	Dec	am	har	20	124

		conducted once at the end of the diagnostic sub-phase if all other diagnostic criteria are met. Variables with residual imbalance across the exposure and referent groups that are associated with the outcome (e.g., baseline Hb) will be included as an independent variable in the subsequent outcome model.	

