9.7.3. Outcome Analysis

Operational definitions for each outcome are described below. Each outcome will be assessed using the primary assessment method for the follow-up period where follow-up will end on the earliest of the following occurrences:

- Disenrollment from health insurance (with a 45-day allowable gap)
- Death
- Discontinuation of voxelotor (with a 45-day allowable treatment gap, voxelotor arm only)
- End of follow-up: up to 1 year from index date (365 days)
- The occurrence of any exclusion criteria events (e.g., pregnancy, stroke, hemodialysis, evidence of HSCT or gene therapy, renal transplant, or liver transplant)

The primary analyses will employ an as-treated follow-up approach that ends follow-up upon treatment changes. Patients will be followed from the index date until treatment change (discontinuation of voxelotor for voxelotor group), or the end of follow-up, whichever is earlier. This as-treated method of analysis allows for an estimate of the effect while the patient is taking the drug of interest and addresses intercurrent events. However, it may introduce bias into the estimates. To adjust for differences in follow-up time between voxelotor patients and their matched controls, matched or pairwise censoring will be applied to censor unexposed on the date of voxelotor discontinuation for their matched pair as a sensitivity analysis.³⁸ A summary of sensitivity analyses is included in Table 7 to evaluate how the magnitude of this bias will be assessed.

Primary Objective - Change in Number of RBC Transfusions PPPY

For each patient, the difference in the number of RBC transfusions PPPY from baseline to follow-up period will be reported as the change and will be calculated as follows:

$$Change = \left(\frac{Number\ of\ RBC\ transfusions\ in\ follow-up}{Available\ days\ of\ follow-up} - \frac{Number\ of\ RBC\ transfusions\ in\ baseline}{365\ days\ *}\right)x\ 365$$

The change in the number of RBC transfusions PPPY will be analyzed using generalized linear model (GLM) with an identity link to estimate the difference in RBC transfusion change rates between the two groups. If any pre-index covariates that are found to be unbalanced after the PS method, it will be included in the regression as a covariate. The rate change and its 95% confidence intervals (CI) will be reported.

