Required 1-year minimum follow-up	Two subgroup analyses have been proposed to evaluate bias introduced by differential follow-up. First, a subgroup analysis of patients with a minimum of 1-year of follow-up will be performed to evaluate the impact of informative censoring.	To address the impact of informative censoring and differential follow-up
Matched censoring	If meaningful differences in follow-up time are observed, matched censoring will be performed to assess the impact of differential follow-up between the exposed and referent group for the primary objective. Bias due to differential follow-up can arise when the reasons for participants dropping out or being lost to follow-up are related to both the treatment and the outcome. Matched censoring mitigates this bias by censoring all patients within a matched set (i.e., patients that have been matched by PS matching) at the earliest time in which a patient in the set was censored. In the context of 1:2 PS matching, where each exposed patient is matched to two referent patients, the matched set will consist of at most three individuals. Thus, matched censoring in this scenario involves censoring data for all three individuals in a matched set at the earliest observed censoring time among them.	To address the impact of informative censoring and differential follow-up
Stratification by number of RBC transfusions in baseline	The number of RBC transfusions PPPY in baseline will be categorized and the primary objective will be reported separately for those categories. This analysis will be performed for all objectives.	To understand the effect of the treatment on high-risk subgroups.
Subgroup analysis by Hb level	The primary analysis will also be performed on a subgroup of patients with Hb values at baseline. A separate PS model will be utilized for this subgroup.	To understand the effect of the treatment on high-risk subgroups and patients with available baseline data.
Subgroup analysis by prior medications	A subgroup analysis will be performed on patients who received hydroxyurea, crizanlizumab, L-glutamine, and/or ESA in baseline the exposed and referent groups.	To understand the effect of other SCD treatments.

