9.9. Strengths and limitations of the research methods

There are some distinct differences between RWE and RCT settings. RWD allows for more generalizable patient populations, but there is less standardization and higher potential for missing values for important patient characteristics (e.g., Hb levels, SCD genotype, comorbidity scores, etc.). Additionally, in an RCT environment, healthcare interactions are on a protocolized schedule for enrolled patients. In RWD, differences exist in how often a patient sees a provider and the type of provider both across groups and within groups, which is why both of these elements will be important for PS modeling. RWD allows for less restrictive inclusion/exclusion criteria and will allow for patients with more severe SCD to be evaluated; for example, all individuals with SCD and recent history of RBC transfusion are excluded from voxelotor clinical trials as well as other medications in development for SCD.

Although there are many benefits to utilizing RWD, there are some inherent limitations. Claims data sources are subject to potential misclassification of the outcome, exposure, or covariates in observational studies (i.e., the presence of a diagnosis code on a medical claim or a generic medication on a prescription claim does not indicate the presence of disease or compliance to treatment given rule out diagnosis or coding errors). 44 The extent of miscoding is believed to be small, as study variables are drawn directly from medical claims that are used for clinical documentation and insurance reimbursement. 44 Additionally, as determined through exploratory analyses, a small proportion of patients have available lab data after linking across all three data sources; Hb will also be excluded from the PS model but will have a separate subgroup analysis because it may be an important confounder in this study. Patients will be excluded from the analysis if they have evidence of stroke in baseline so that patients receiving chronic transfusions for secondary stroke prevention are not included in the analysis. Although patients may also receive transfusions for primary stroke prevention, claims data will not have information on transcranial doppler velocity, and thus such patients will not be identifiable. However, this is estimated to be a small portion of patients within the study (less than 5% of pediatric patients with SCD receive chronic transfusions). 45

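### One 0.10 ASD threshold decides whether the baseline transfusion count enters the PS, counts as balanced and enters the primary GLM, so arms with similar means but offsetting shapes can go unadjusted

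*Protocol*

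**What the plan says.** Three statements in the protocol act on the baseline RBC transfusion count.

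- **Entry to the PS (9.7.2, PS Estimation):** "Covariates with an ASD > 0.1 will be considered imbalanced and will be included in a PS model fit using logistic regression".
- **Passing the diagnostic (9.7.2, Table 6, diagnostic 3):** "Covariate balance will be defined as an ASD ≤ 0.10".
- **Entry to the primary model (9.7.3, Primary Objective):** a baseline covariate is added to the GLM when imbalance remains once the PS step is done; nothing there adds one that has passed.

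Table 4 (9.3) summarises the count as "Continuous: Mean (SD); Median (IQR); Minimum; Maximum". The protocol gives no ASD formula; for a variable in this form it is normally the standardized difference in means. Section 9.7.2 states no numerical criterion for variance ratios, categories or distributions.

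Two other provisions touch on the point. Section 9.7.2 says "Demographics and baseline clinical characteristics of patients within each study group will be described before and after the applications of PS adjustment". Table 7 plans a stratified analysis: "The number of RBC transfusions PPPY in baseline will be categorized and the primary objective will be reported separately for those categories". It does not state the categories.

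**The concern.** The baseline count is not an ordinary covariate. The primary outcome in 9.7.3 is the follow-up rate minus the baseline rate, and Table 2 admits only patients with at least two baseline transfusions, so regression to the mean is built in.

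How far a patient regresses depends on the kind of patient. Section 7 describes "chronic transfusions, usually administered monthly", which is about 12 a year and should change little without a drug effect. A patient with 5-8 unplanned transfusions in the baseline year is likely to have fewer the next year, and one who just met the minimum of two changes little. Section 9.9 says that baseline stroke is excluded so as to remove secondary-prevention patients, but that primary-prevention patients cannot be identified. Scheduled and episodic patients can therefore both be present.

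If expected change is non-linear in the count, equal means do not ensure equal expected change. A count whose means agree but whose shape differs stays out of the PS, passes Table 6 and stays out of the GLM. At stake is a spurious difference in the primary estimate that the protocol's own rule would not flag.

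**Working it through.** **1. The plan's own figure.** Section 9.5 gives 185 treated and 370 controls, SD 3.0, difference 1, variance factor 1.65 and 80% power. Two-sided 5% is assumed.

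- SE = 3.0 × √(1/185 + 1/370) = 0.270.
- With the factor: 0.270 × √1.65 = 0.347.
- Power = Φ(1/0.347 − 1.96) = 82%. The stated 80% is reproduced, slightly on the safe side, and is not disputed. These SEs are used in step 5.

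**2. Expected change by baseline count, no drug effect.** Assumed model: episodic patients gamma-Poisson, monthly patients about 12 a year, entry at two or more, full-year follow-up. In a pool with 16% monthly patients:

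| Baseline count | 2 | 3 | 4 | 5 | 6 | 8 | 10 | 12 |
|---|---|---|---|---|---|---|---|---|
| Expected change | 0.25 | 0.00 | −0.24 | −0.50 | −0.76 | −1.09 | −0.17 | −0.43 |

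The relation is neither linear nor monotone. As an extreme illustration of mechanism only, put one arm entirely at 6 and split the other 60% at 2 and 40% at 12. Both means are 6 (0.6 × 2 + 0.4 × 12), so the ASD is 0. Expected changes are −0.76 and 0.6 × 0.25 + 0.4 × (−0.43) = −0.02.

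**3. A different share of monthly patients alone.** Keep the counts within each class the same in both arms. An ASD of 0.10 with a baseline SD of about 4.1 allows a mean gap of 0.41. With class means of 12 and 5.0, the share gap is at most 0.41/7.0 = 5.9 points. Episodic patients change by −0.50 on average and monthly patients by about 0, so the spurious difference is 0.059 × 0.50 = 0.03 PPPY. A pool with 31% monthly patients gave 5.4 points and 0.03. The ASD rule handles this case.

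**4. Offsetting differences at equal means.** One arm has fewer monthly patients but higher-count episodic patients.

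| Gap in monthly share | Spurious difference (PPPY) |
|---|---|
| 5 points | −0.11 to −0.18 |
| 10 points | −0.22 to −0.36 |
| 15 points | −0.34 to −0.55 |

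With 185/370 and a 10-point gap, 74% of samples passed ASD ≤ 0.10, about the same as with no gap (73%).

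A milder mechanism is that patients at 5-8 are 1.5 to 3 times as likely to start voxelotor. It was simulated with 16-20% monthly patients and 1:2 PS matching, under several sets of assumptions. The bias ran from about −0.03 to −0.22, and the count passed the ASD rule in 94-100% of runs. In one set its ASD was already at or below 0.10 before matching in about 80% of runs, so it would not have entered the PS. The sign reverses if starters come from the extremes.

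**5. Effect on the 5% error.** For bias b, the rejection probability is Φ(b/SE − 1.96) + Φ(−b/SE − 1.96).

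| b | SE 0.270 | SE 0.347 |
|---|---|---|
| 0.03 | 5.1% | 5.1% |
| 0.10 | 6.6% | 6.0% |
| 0.22 | 12.9% | 9.7% |
| 0.36 | 27% | 18% |

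**6. What adjustment does.**

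- Under selection at 5-8, a linear baseline term left the bias unchanged (−0.115 against −0.117).
- Category terms in the GLM brought it within 0.02. Cut-points not aligned with the selection left up to −0.05.
- In the 10-point scenario, three categories (2-3, 4-8, 9 or more) reduced −0.36 only to −0.28.
- At least one category ASD exceeded 0.10 in 93% of the 10-point samples that passed on the mean. It also did so in 36% (47% in another simulation) of samples whose arms were truly alike.

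**The case against.** The strongest reply is that this is a general limit of a standard diagnostic and that functional form and distributional checks belong in the SAP, to which 9.7.2 refers. The protocol fixes no linear term, and the Abstract names prior transfusions among the covariates for PS modeling. This stands in part: the SAP may add diagnostics. But the Abstract's list also names Hb, which 9.3 removes from the PS, so it reads as a list of candidates. The threshold that governs entry and balance is stated in the protocol itself.

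Second, safeguards exist. SD, median and IQR are reported before and after the PS, the study team confirms the diagnostics, and Table 7 reports the primary objective by baseline category. A gross difference, such as the illustration in step 2, would show in the SD. The shifts in step 4 leave the SDs nearly equal (4.09 against 3.93 in one scenario). None of these summaries is a pass criterion, and the strata do not alter the primary estimate.

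Third, other PS-eligible covariates, such as iron overload and chelation, may mark chronic transfusion. In one simulation, adding an assumed chelation-type proxy moved the bias from −0.08 to between −0.035 and −0.06. This reduces the problem without removing it.

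Fourth, the monthly share is unknown. Section 9.9 says "less than 5% of pediatric patients with SCD receive chronic transfusions". Set against the roughly 20% of all SCD patients transfused in the past year (9.2), that suggests at most about 5/20 = 25% of transfused patients. This is rough, because the populations differ and this study requires two transfusions.

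**Conclusion.** The weakness is real but modest. One mean-based threshold controls PS entry, the balance decision and GLM entry for a covariate that is part of the outcome, so offsetting differences in shape can go unadjusted. With 1.5- to 3-fold selection at 5-8 the spurious difference is about 0.03 to 0.2 PPPY, at most about a fifth of the 1-unit target, with little to moderate inflation of the 5% error. Offsetting mix differences of 5 to 15 points gave about 0.1 to 0.5. All sizes rest on assumed transfusion distributions and selection patterns.

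Three stronger readings are not supported.

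- A reader might infer that any difference in the share of monthly patients can pass and bias the result. Step 3 shows that the share alone is held to about 5-6 points and 0.03-0.04 PPPY. Material bias needs an offsetting shift in episodic counts.
- A reader might infer a bias in favour of voxelotor. The protocol does not say which patients start, and the sign reverses under other patterns.
- A reader might infer an error rate of about 20%. At a bias of 0.22 that requires an SE near 0.2; the protocol's planning figures give 10-13%.

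**What to change.** - **9.7.2:** always include the baseline RBC transfusion count in the PS, whatever its ASD, in flexible form: the Table 7 categories, specified in advance, or a spline.
- **9.7.3:** always include the same terms in the primary GLM.
- **Table 6, diagnostic 3:** report the ASD for each count category after the PS. A value above 0.10 should prompt another PS iteration or matching on category. It should not be a hard pass/fail rule, because chance alone exceeds 0.10 in over a third of truly alike samples.

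The cost is a few extra coefficients and possibly a few unmatched patients. No new data are needed, and the count distributions can be compared between arms before any outcome is viewed. Categories reduce the bias but do not fully remove it if the mix of scheduled and episodic patients differs within a category; the report should say so.
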